## **8.1 Screening**

Patients in the Run-In Cohort should have a *P. falciparum* parasitemia of  $\geq 1,000$  and  $\leq 150,000$  parasites/ $\mu\text{L}$  at the time of pre-screening.

Patients in Cohort 1 and Cohort 2 should have a *P. falciparum* parasitemia of  $\geq 1,500$  and  $\leq 150,000$  parasites/ $\mu\text{L}$  at the time of pre-screening.

It is not permissible to re-screen a patient within the same malaria episode if s/he fails the initial pre-screening or screening. Re-screening of a patient may occur in case the patient is returning to the study site for a new malaria episode. A new study number will be issued to the patient.

### **8.1.1 Information to be collected on screening failures**

Patients who sign an informed consent form and subsequently found to be ineligible will be considered a screen failure. The reason for screen failure should be entered on the applicable CRF. The demographic information, informed consent, and Inclusion/Exclusion pages must also be completed for screen failure patients. No other data will be entered into the clinical database for patients who are screen failures, unless the patient experienced a serious adverse event during the screening phase (see SAE section for reporting details). Adverse events that are not SAEs will be followed by the investigator and collected only as source data.

Patients who sign an informed consent and are considered eligible but fail to be started on treatment for any reason will be considered an early terminator. The reason for early termination should be captured on the appropriate CRF.

## **8.2 Patient demographics/other baseline characteristics**

Country-specific regulations should be considered for the collection of demographic and baseline characteristics in alignment with CRF.

Patient demographic and baseline characteristic data to be collected on all patients include:

- Age
- Gender
- Child bearing potential for females (post first menarche)
- Body weight
- Body height
- Body temperature
- Initial medical and treatment history
- Signs and symptoms of severe malaria
- Vital signs
- Physical exam
- Prior and concomitant medications
- Blood chemistry and hematology as specified above
- Thyroid function
- Urinalysis

- Pregnancy test (Run-in Cohort only)
- Malaria blood film for asexual parasite [REDACTED] counts and species differentiation
- Blood sampling for parasite genotyping
- Medical history/current medical conditions
- Triplicate 12-lead ECG
- PK sampling for Run-in Cohort

Investigators will have the discretion to record abnormal test findings on the medical history CRF whenever in their judgment, the test abnormality occurred prior to the informed consent signature.

### 8.3 Efficacy

Efficacy assessments will be based on the PCR-corrected and uncorrected Adequate Clinical and Parasitological Response (ACPR) at Days 15, 29 and 43, the incidence rate of recrudescence and reinfection at Days 15, 29 and 43, and the PCT and FCT.

#### 8.3.1 Parasitemia assessment (details provided in the Laboratory Manual)

[figure not shown]
Blood sampling for parasitology can be done by means of finger prick except when the timing for parasitology assessments coincide with time for clinical laboratory tests, in which case, blood sample can be taken from the venous blood collected for clinical laboratory analyses.

##### Parasite counts:

- Giemsa stained thick (and thin) films will be examined. Thin films will be examined only if identification of species is needed after malaria (*Plasmodium*) parasite is detected in a thick film
- Examination with binocular microscope and with oil immersion lens at 1,000 magnification
- Pre-screening/screening examination (prior to patient inclusion into the trial), thick film:
  - at least 200 thick film fields are examined. If there is no malaria parasite, the slide is declared negative, and the patient is not suitable for inclusion.
  - if asexual forms of *P. falciparum* are found, a total of 200 thick film fields are to be screened for *Plasmodium* species other than *P. falciparum*.
  - when it has been ascertained that *P. falciparum* is present, a count is made of the asexual forms [REDACTED] against leukocytes, using a tally counter. Counting needs to be done based on at least 200 leukocytes according to the WHO standards. If less than 100 parasites, counting will be extended to 500 leukocytes. The parasite density will be calculated according to the formula:

Number of *Plasmodium* parasites x actual leukocytes (WBC)

Parasite density per  $\mu\text{l}$  = 
$$\frac{\text{Number of } Plasmodium \text{ parasites} \times \text{actual leukocytes (WBC)}}{\text{Number of leukocytes (WBC) counted (200)}}$$

- Blood examination during the 43-day trial period:
  - a total of 200 thick films fields are examined (tally counter) before a slide can be pronounced negative
  - if asexual forms of *P. falciparum* are present, a parasite count is required
  - if *Plasmodium* species other than *P. falciparum* are found, note species
  - [REDACTED]

The count should be made for each species [REDACTED]  
(White et al 2014). [REDACTED]

[REDACTED]. Thick (and thin blood) films will be prepared as specified in the assessment schedule table and evaluated by standard techniques (Giemsa stain and light microscopy). This will be the definitive test for a positive *P. falciparum* infection. The parasite counts can also be quantified in percentage (per 1,000) of red cells on the thin film.

[REDACTED]

### 8.3.2 Blood sample for molecular diagnostic purposes

Blood will be sampled for parasite genotyping as indicated in the assessment schedule (Table 8-1, Table 8-2, Table 8-3). At screening, a blood sample will be collected from all patients fulfilling eligibility criteria for inclusion in the study. A second blood sample collected as per assessment schedule will be analyzed only in patients showing treatment failure. This will be used to distinguish between recrudescence and new infection. Molecular analysis will be done by a pre-selected central laboratory.

[REDACTED]

[REDACTED]

### 8.3.3 Appropriateness of efficacy assessments

The microscopy examination methods to quantify the malaria parasite [REDACTED] in blood are validated methods (Sinden et al 2012, White et al 2014). For full details refer to the Laboratory Manual.

## 8.4 Safety

Clinical adverse events will be monitored throughout the study to assess the general safety and tolerability of the treatment groups.

Safety assessments are specified below with the assessment schedule detailing when each assessment is to be performed.

For details on AE collection and reporting, refer to AE section (Section 10.1).

[REDACTED]

As per [Section 4.6](#), during a Public Health emergency as declared by Local or Regional authorities i.e. pandemic, epidemic or natural disaster, that limits or prevents on-site study visits, regular phone or virtual calls can occur as per the visit schedule or more frequently for safety monitoring and discussion of the participant's health status until it is safe for the participant to visit the site again.

**Table 8-4 Assessments & Specifications**

Assessment	Specification
Physical examination and malaria signs and symptoms	
A complete physical examination will be performed by the investigational staff at screening and will include the examination of general appearance, skin, neck (including thyroid), eyes, ears, nose, throat, lungs, heart, abdomen including splenomegaly, back, lymph nodes, extremities, vascular and neurological. In addition, body height in centimeters (cm) and body weight to the nearest 0.1 kilogram (kg) in indoor clothing, but without shoes will be measured during the complete physical examination at screening.
 
An abbreviated physical examination will be performed at all other visits starting from Day 1 including the examination of general appearance and vital signs. Body weight to the nearest 0.1 kilogram (kg) in indoor clothing, but without shoes will be measured at Study End only (Day 43 or earlier in case of premature patient withdrawal from study participation). Body height in centimeters (cm) will be also measured at Study End in Cohort 2.
 
A full assessment of malaria signs and symptoms will be made alongside the physical examinations at time points described in the assessment schedule for all patients table (Table 8-1). In particular, pediatric patients need to be examined for signs of dehydration.
 
Information for all physical examinations must be included in the source documentation at the study site. Body height and body weight must be recorded in the clinical database. Clinically relevant findings that are present prior to signing informed consent must be included in the Medical History part of the eCRF. Significant findings made after the first administration of investigational drug which meet the definition of an Adverse Event must be recorded on the Adverse Event section of the eCRF.

Vital signs	
Vital signs (blood pressure, body pulse) will be monitored as part of the physical exam as indicated in the study assessment schedule table and recorded on the clinical database.
 
After the patient has been in supine position for five minutes, systolic and diastolic blood pressure will be measured three times using an automated validated device, e.g. OMRON, with an appropriately sized cuff. The repeat measurements will be made at 1 - 2 minute intervals and the mean of the three measurements will be used. The same arm must be used throughout the study. A sphygmomanometer with an appropriately sized cuff should be used.

Body temperature	
Body temperature will be monitored as indicated in the study assessment schedule table and recorded on the clinical data base. Fever monitoring will be done every 6 hours until resolution of fever, defined as being afebrile for 24 hours.
 
Fever clearance is defined (in patients with an increased temperature at baseline) as the time of the first measurement of axillary temperature of < 37.5°C (or < 38.0°C for alternative routes). Fever clearance will be concluded following confirmation of temperature < 37.5°C (or < 38.0°C for alternative routes) on the subsequent measurement for at least 24 hours.
 
Patients who entered in the study on the basis of history of fever and did not subsequently have an increased body temperature measurement indicating presence of fever pre-dose will not be included in the analysis of FCT.

### 8.4.1 Laboratory evaluations

A local laboratory or a micro-sampling device can be used for analysis of safety labs (hematology, blood chemistry, and urinalysis). Blood sampling volumes should be collected as per the laboratory manual. The number of samples/blood draws and total blood volume collected will remain under the limits recommended in this population (Howie 2011). Based on the outcomes of the Run-in cohort and study CKAF156A2202, laboratory evaluations done (Table 8-5) and the frequency of blood draws (Table 8-2 and Table 8-3) may be reduced in patients <12 years old (Cohorts 1 and 2). If this is the case, all investigators will be informed before the start of Cohort 1.

A central laboratory will be used for PCR (parasite identification [REDACTED]), ECG, and PK measurements. Details on the collections, shipment of samples and reporting of results by the central laboratories are provided to investigators in the laboratory manuals where applicable.

Assessments will be done as indicated in the study assessment schedule tables.

Clinically notable laboratory findings are defined in Section 16.1.

[figure not shown]
**Table 8-5 Local laboratory evaluations**

Test Category	Test Name
Hematology	Hemoglobin, hematocrit (packed-cell volume - PCV), platelets, white blood cell (WBC) count with differential (as much as possible, neutrophil, lymphocyte and eosinophils counts will be performed while basophils and monocytes can be aggregated as 'other'). Red blood cell count (RBC), reticulocyte count and haptoglobin levels will be performed in case of significant hemoglobin drop > 2g/dL or hemoglobin levels ≤ 5g/dL (will be optional depending on site equipment).
Chemistry	
Routine blood chemistry testing will be performed according to the visit schedule in order to monitor the general medical condition of the patient.
 
This includes: Glucose, creatinine (serum), transaminases (ALT/Serum glutamic pyruvic transaminase (SGPT) and AST/Serum glutamic oxaloacetic transaminase (SGOT)), serum-γ-glutamyl transferase (GGT), Total and direct bilirubin, Alkaline Phosphatase (ALP), Blood Urea Nitrogen (BUN), prothrombin time International Normalized Ratio (INR), sodium, potassium, magnesium, calcium, chloride, total protein and albumin.
 
Thyroid stimulating hormone (TSH) and free thyroxine T4 are tested at screening, Day 15 and at study completion only.
 
At screening, results of the thyroid test are not mandatory for eligibility into the study.

Urinalysis	Dipstick measurements for specific gravity, protein, glucose and hematuria. Microscopy will be performed and urine sediment will be assessed in case of an abnormal dipstick test.

### 8.4.2 Electrocardiogram

ECGs should be taken in triplicate within 5 minutes (after 10 minutes rest in the supine position to ensure a stable heart rate according to the ECG investigator manual). The preferred sequence of cardiovascular data collection during study visits is ECG collection first, followed by vital signs, and blood sampling.

The Fridericia QT correction formula (QTcF) must be used for clinical decisions, e.g. at the Screening visit(s) to assess eligibility.

Triplicate 12 lead ECGs are to be collected with ECG machines supplied by the central laboratory and recorded approximately 2 minutes apart. The mean QTcF value for each visit will be calculated from the triplicate ECGs for each participant. Initial manual readout will be done locally in order to detect significant safety findings and allow for immediate response if needed. Local readout will be used for inclusion/exclusion purposes as central readout is not available within 24 hours. Additional, unscheduled, safety ECGs may be repeated at the discretion of the investigator at any time during the study as clinically indicated.

In the event that a clinically significant ECG abnormality is identified at the site (e.g., severe arrhythmia, conduction abnormality of QTcF > 500 ms) the SAE must be reported according to the procedure described in [Section 10.1.2](#). If the patient is hemodynamically compromised, the investigator or a medically qualified person must initiate appropriate safety procedures without delay (for example cardioversion).

If QTcF is > 500 ms or QTcF increases  $\geq 60$  ms from baseline occur at any time, the patient should be assessed at the site and appropriate safety procedures (e.g., blood sampling and electrolyte correction) initiated without delay, if required. In addition two additional ECGs should be collected at 2-min intervals and provided to the central ECG laboratory for confirmation.

Clinically significant abnormalities must be recorded on the relevant section of the medical history/Current medical conditions/AE eCRF page as appropriate.

Any post-dose average QTcF > 500 ms will result in patient discontinuation from the treatment if there is a planned subsequent treatment.

[figure not shown]
Assessments will be done as indicated in the study assessment ([Table 8-1](#)). All ECGs will be assessed centrally by an independent and blinded (with age of patient identified) cardiologist.

#### **8.4.3 Pregnancy and assessments of fertility in Run-in Cohort**

A pregnancy test in urine will be performed at the screening visit and at study completion in the Run-in Cohort.

Patients of child-bearing potential are defined as all females physiologically capable of becoming pregnant. This includes female pediatric patients who are menarchal or who become menarchal during the study. Serum pregnancy test will be performed for all females of child-bearing potential according to the protocol assessment schedule (See [Table 8-1](#)).

All menarchal girls and their parents/caregivers should be informed about the potential risks of pregnancy and the need to prevent pregnancy during the study treatment. It is important to be sensitive in introducing this issue, as understanding and comprehension of puberty, sexual activity, pregnancy and contraception is influenced by age, as well as factors such as precocity, socio (educational) economic and familial background. These discussions with the patient and her parents/caregivers are therefore best performed by investigators familiar with the pediatric patient and her family and should be guided by requirements of the local regulatory authorities. These discussions should take into account the socio-economic, cultural factors and religious beliefs of the adolescent participant and her family. The investigator should also discuss the management of the pregnancy test results with the patient and her parents/caregivers. The privacy of the patient should be considered in accordance with the local law and ethics.

Additional pregnancy tests may be performed at the investigator's discretion during the study. Patients becoming pregnant must be discontinued from study drug. However, a patient may choose to remain in the study should she become pregnant, and be followed according to the protocol-defined study visits.

#### **8.4.4 WHO Definitions of treatment failures and Adequate Clinical and Parasitological Response**

##### **Early Treatment Failures (ETF)**

- Development of danger signs or severe malaria on Day 2, Day 3, Day 4 in the presence of parasitemia.
- Parasitemia on Day 3 higher than Day 1 count irrespective of axillary temperature.
- Parasitemia on Day 4 with axillary temperature  $\geq 37.5^{\circ}\text{C}$ .
- Parasitemia on Day 4 equals to or more than 25% of count on Day 1.

##### **Late Clinical Failure (LCF)**

- Development of danger signs or severe malaria on any day from Day 5 to Day 43 in the presence of parasitemia without previously meeting any of the criteria of ETF.
- Presence of parasitemia and axillary temperature  $\geq 37.5^{\circ}\text{C}$  on any day from Day 5 to Day 43 without previously meeting any of the criteria of ETF.

##### **Late Parasitological Failure (LPF)**

- Presence of parasitemia on any day from Day 8 to Day 43 and axillary temperature  $< 37.5^{\circ}\text{C}$  without previously meeting any of the criteria of ETF or LCF.

##### **Adequate Clinical and Parasitological Response (ACPR):**

Absence of parasitemia on Day 43 irrespective of axillary temperature, without previously meeting any of the criteria of ETF or LTF or LPF.

[figure not shown]
In this study, “absence of parasitemia on Day 43” has been adapted to “absence of parasitemia on Day 29” based on the short half-life of the study drugs.

Note: The first day of treatment with study medication is defined as Day 1 while the day prior to the first day of treatment is defined as Day -1. Compared to [WHO 2015](#) which defined Day 0 as the first day of treatment with study medication, days after treatment referred to in this protocol are 1 day greater. For example, Day 29 in this protocol corresponds to Day 28 by [WHO 2015](#).

See [Section 16.4](#) for signs/symptoms indicative of severe/complicated malaria

#### **8.4.5 Appropriateness of safety measurements**

The safety assessments selected are standard for this indication/patient population.

## 8.5 Additional assessments

### 8.5.1 Pharmacokinetics

PK samples will be collected at the visits defined in the assessment schedule ([Table 8-1](#), [Table 8-2](#), [Table 8-3](#)). Follow instructions outlined in the laboratory manual regarding sample collection, numbering, processing, and shipment.

The number of samples/blood draws and total blood volume collected should not exceed those stated in the protocol and laboratory manual.

Pharmacokinetic (PK) samples will be obtained and evaluated in all patients. KAF156 and lumefantrine exposures will be determined by a validated LC-MS/MS method; the anticipated Lower Limit of Quantification (LLOQ) is 5 and 50 ng/mL for KAF156 and lumefantrine, respectively.

KAF156 and lumefantrine concentrations will be expressed in mass per volume units and will refer to the free base. Concentrations below the LLOQ will be reported as “zero” and missing data will be labeled as such in the Bioanalytical Data Report.

Pharmacokinetic (PK) samples will be obtained and evaluated in all patients at all dose levels/regimen. Parameters such as AUC, Cmax, Tmax, C168 (Day 8 concentration.) etc. will be determined using non-compartmental method for both KAF156 and LUM.

## 9 Study discontinuation and completion

### 9.1 Discontinuation

#### 9.1.1 Discontinuation of study treatment

If discontinuation of study treatment occurs, the investigator should make a reasonable effort to understand the primary reason for the patient's premature discontinuation of study treatment and record this information. Patients who discontinue from study treatment agree to return for end of treatment follow-up visits indicated in the Assessment Schedule (refer to [Section 8](#)).

If the patient cannot or is unwilling to attend any visit(s), the site staff should maintain regular telephone contact with the patient, or with a person pre-designated by the patient. This telephone contact should preferably be done according to the study visit schedule.

Patients will be treated under hospital supervision during the treatment period. Discontinuation of study treatment for a patient occurs when study drug is permanently stopped earlier than the

protocol planned duration, and discontinuation can be initiated by either the patient or the investigator.

The investigator must discontinue study treatment for a given patient if, on balance, he/she believes that continuation would negatively impact the patient's risk of trial participation.

Study treatment must be discontinued under the following circumstances:

- Patient request
- Pregnancy
- Use of prohibited treatment as per recommendations in [Table 6-4](#)
- Any situation in which continued study participation might result in a safety risk to the patient and/or any adverse events that in the judgment of the investigator, taking into account the patient's overall status, prevent the patient from continuing participation in the study
- Unsatisfactory therapeutic effect
- Emergence of the following adverse events: severe nausea/vomiting, severe pruritus, increases in QTcF to > 500 ms (based on repeat ECGs), development of ventricular arrhythmia or clinically significant (symptomatic) bradycardia.
- Any laboratory abnormalities that in the judgement of the investigator, taking into consideration the patient's overall status, prevent the patient from continuing participation in the study (e.g., increase in liver enzymes > 3 times the upper limit of normal (see [Section 16.2](#)))
- Deviation from the planned dose regimen for the study drug (e.g., vomiting of the replacement dose within 2 hours of intake)

[figure not shown]
Patients who discontinue study drug for any of the above reasons may be given rescue medication at the discretion of the investigator and will be followed for the whole study duration until Day 43.

The investigator must also contact the IRT to register the patient's discontinuation from study treatment (this patient will not be replaced).

If a patient is tested positive to COVID19 during the course of the study, the patient may not be available for laboratory or clinical evaluation (as per the local guidelines in management of COVID19). However, all the efforts should be made to follow the patients for safety until end of the study. In case of non-availability, the patient should be considered as discontinued from the study with COVID19 as the reason for discontinuation.

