#### **6.1.4 Treatment duration**

The duration of the treatment with KAF156/LUM-SDF will be two days (once daily/QD) for an individual patient in the Run-in Cohort.

The duration of treatment with KAF156/LUM-SDF in Cohorts 1 and 2 will be either two days or three days once daily/QD, depending on the outcome of the of the Run-in Cohort and KAF156A2202 study.

Coartem® will be given twice a day (BID) for three days as per the product label.

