**Table 16-3 Follow-up requirements for liver events and laboratory triggers**

Criteria	Actions required	Follow-up monitoring
Potential Hy's Law case a	
 
Discontinue the study drug immediately
 
Repeat LFTs within 24h
 
Hospitalize, if clinically appropriate
 
Establish causality
 
Report to Novartis as an SAE
 
	ALT, AST, TBL, Alb, PT/INR, ALP and GGT until resolution c (frequency twice a week until resolution, stabilize or return to within baseline values)
ALT or AST		
> 8 x ULN	
 
Discontinue the study drug immediately
 
Repeat LFTs within 24h
 
Hospitalize if clinically appropriate
 
Establish causality
 
Report to Novartis as an SAE
 
	ALT, AST, TBL, Alb, PT/INR, ALP and GGT until resolution c (frequency twice a week until resolution, stabilize or return to within baseline values)
> 3 x ULN and INR > 1.5	
 
Discontinue the study drug immediately
 
Repeat LFTs within 24h
 
Hospitalize, if clinically appropriate
 
Establish causality
 
Report to Novartis as an SAE
 
	ALT, AST, TBL, Alb, PT/INR, ALP and GGT until resolution c (frequency twice a week until resolution, stabilize or return to within baseline values)
> 5 to ≤ 8 x ULN	
 
Repeat LFT within 24 hours
 
	ALT, AST, TBL, Alb, PT/INR, ALP

Criteria	Actions required	Follow-up monitoring
	
 
If elevation persists, continue follow-up monitoring
 
If elevation persists for more than 2 weeks, discontinue the study drug
 
Establish causality
 
Report to Novartis as an SAE
 
	and GGT until resolution c (frequency twice a week until resolution, stabilize or return to within baseline values)
> 3 × ULN accompanied by symptoms b	
 
Discontinue the study drug immediately
 
Repeat LFT within 24 hours
 
Hospitalize if clinically appropriate
 
Establish causality
 
Report to Novartis as an SAE
 
	ALT, AST, TBL, Alb, PT/INR, ALP and GGT until resolution c (frequency twice a week until resolution, stabilize or return to within baseline values)

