> 3 to ≤ 5 × ULN (patient is asymptomatic)	
 
Repeat LFT within 24 hours
 
If elevation is confirmed, initiate close observation of the patient
 
	Monitor LFT until resolution c (frequency twice a week until resolution, stabilize or return to within baseline values)
ALP (isolated)		
> 2 × ULN (in the absence of known bone pathology)	
 
Repeat LFT within 24 hours
 
If elevation persists, establish causality
 
	Monitor LFT until resolution c (frequency twice a week until resolution, stabilize or return to within baseline values)
TBL (isolated)		
> 2 × ULN (in the absence of known Gilbert syndrome)	
 
Repeat LFT within 24 hours
 
If elevation persists, discontinue the study drug immediately
 
Hospitalize if clinically appropriate
 
Establish causality
 
	ALT, AST, TBL, Alb, PT/INR, ALP and GGT until resolution c (frequency twice a week until resolution, stabilize or return to within baseline values) Test for hemolysis (e.g., reticulocytes, haptoglobin, unconjugated (indirect) bilirubin)
> 1.5 to ≤ 2 × ULN (patient is asymptomatic)	
 
Repeat LFT within the next week
 
If elevation is confirmed, initiate close observation of the patient
 
	Investigator discretion Monitor LFT within 1 to 4 weeks or at next visit
Jaundice	
 
Discontinue the study drug immediately
 
Hospitalize the patient
 
Establish causality
 
Report to Novartis as an SAE
 
	ALT, AST, TBL, Alb, PT/INR, ALP and GGT until resolution c (frequency twice a week until resolution, stabilize or return to within baseline values)

Criteria	Actions required	Follow-up monitoring
Any AE potentially indicative of a liver toxicity* severe events only SMQ AE	
 
Consider study drug discontinuation
 
Hospitalization if clinically appropriate
 
Establish causality
 
Report to Novartis as an SAE
 
	ALT, AST, TBL, Alb, PT/INR, ALP and GGT until resolution c (frequency twice a week until resolution, stabilize or return to within baseline values)

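### For symptom-free AST/ALT rises above 3 and up to 8 × ULN, protocol Section 9.1.1 and Table 16-3 are not aligned on stopping treatment, and the table's 2-week condition cannot be met in a 2–3 day course

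*Protocol*

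**What the plan says.** **Section 9.1.1** opens its list with "Study treatment must be discontinued under the following circumstances". The laboratory item in that list is conditional: "Any laboratory abnormalities that in the judgement of the investigator, taking into consideration the patient's overall status, prevent the patient from continuing participation". Its only example is an "increase in liver enzymes > 3 times the upper limit of normal", and it refers the reader to Section 16.2.

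**Table 16-3**, in Section 16.2, sets the required action for each AST/ALT band:
- Above 3 and up to 5 × ULN, asymptomatic patients only: repeat the test within 24 hours, then "If elevation is confirmed, initiate close observation of the patient". No stop is mentioned.
- Above 5 and up to 8 × ULN: repeat the test, monitor and report as an SAE. "If elevation persists for more than 2 weeks, discontinue the study drug".
- Immediate discontinuation for "> 3 × ULN accompanied by symptoms", above 3 × ULN with INR above 1.5, a potential Hy's Law case, or above 8 × ULN.

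**Section 10.2.1** refers to Table 16-3 for the actions required in a liver event. It also lists discontinuation where appropriate, and for that it sends the reader back to the discontinuation section.

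**Section 6.1.4** fixes the course length. KAF156/LUM-SDF in Cohorts 1 and 2 "will be either two days or three days once daily/QD", and Coartem is given twice daily for three days. The Run-in Cohort receives two days.

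**The concern.** An investigator holding a result of, say, 4 or 6 × ULN in a child who feels well finds two messages. Section 9.1.1 presents more than 3 × ULN as the typical laboratory reason to stop. The table it cites says to observe, or to wait for a duration that the course never reaches. The cross-references run in a circle (9.1.1 to 16.2, and 10.2.1 to both), so following them does not settle the question.

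The question can arise in practice. Exclusion criterion 13 names AST/ALT above 3 × ULN, so a child with normal bilirubin may enter just below that level, and a small rise then reaches the 9.1.1 example.

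Two things are at stake. The first is a safety instruction that cannot operate as written, in a band that Table 16-2 classes as a liver event above 5 × ULN. The second is consistency between sites. In an open-label trial whose primary test is run on the PPS, a stop under one passage and continuation under the other can decide whether a child is analysed.

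**Working it through.** **1. Passages side by side** (AST/ALT, with no symptoms, INR above 1.5 or Hy's Law features)

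| Band | Section 9.1.1 | Table 16-3 |
|---|---|---|
| > 3 to 5 × ULN | Meets the example; stop if the investigator judges that the child cannot continue | Repeat, then observe; no stop |
| > 5 to 8 × ULN | As above | Stop only after more than 2 weeks |
| > 8 × ULN | As above | Stop immediately |

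The first two rows are not aligned. Above 8 × ULN, or above 3 × ULN with symptoms, INR above 1.5 or Hy's Law features, the table also stops treatment, so the two places agree in direction.

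**2. Can the 2-week condition be met during dosing?** Two weeks is 14 days: 14/2 = 7 times a 2-day course and 14/3 = 4.7 times a 3-day course. Counting from the Day −1 screening sample changes nothing. The condition cannot be met while drug is being given in either arm.

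**3. When can a result still affect dosing?** Chemistry is scheduled at screening, 24 h and 48 h (Tables 8-2 and 8-3).
- 2-day KAF156/LUM-SDF: only the 24 h pre-dose sample can matter, and only if it is reported before the second and last dose. The 48 h sample comes after treatment.
- 3-day KAF156/LUM-SDF: the 24 h and 48 h samples, both pre-dose.
- Coartem (doses at 0, 8, 24, 36, 48 and 60 h): the 24 h and 48 h samples.

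Result turnaround is not stated, and footnote 13 to both tables allows fewer draws in Cohorts 1 and 2.

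**4. Effect on the PPS.** The PPS needs at least 80% of study medication (protocol Section 12.1; SAP Section 2.2 and Table 5-14). SAP Section 2.4.1 defines compliance as doses taken divided by doses planned, averaged over KAF156 and LUM-SDF. Its worked example reproduces: 600/800 = 75% and (75% + 100%)/2 = 87.5%. Applied to a stop of all study drug:

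| Course | Doses taken | Compliance | 80% rule |
|---|---|---|---|
| KAF156/LUM-SDF, 2-day | 1 of 2 | 50% | fails |
| KAF156/LUM-SDF, 3-day | 1 of 3 | 33.3% | fails |
| KAF156/LUM-SDF, 3-day | 2 of 3 | 66.7% | fails |
| Coartem | 4 of 6 or fewer | 66.7% or less | fails |
| Coartem | 5 of 6 | 83.3% | passes |

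The Coartem 83.3% case keeps the child in the PPS only if no non-study antimalarial is given during the treatment period, because Table 5-14 excludes for that separately.

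**5. Scale.** The plan states at least 87% power with 92 per group, 95% response in both groups and a 10% margin. With unpooled variance, SE = √(2 × 0.95 × 0.05/92) = 0.0321, and power = Φ(0.10/0.0321 − 1.96) = 87.5%, which agrees. Also 220 × 0.84/2 = 92.4 per group. The documents give no frequency for AST/ALT in this range, so extra PPS losses are an assumption. Losing 1, 2 or 5 more per group gives 87.2%, 86.8% or 85.7%.

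**The case against.** The strongest reply is that no formal contradiction exists. The 9.1.1 item applies only where the investigator judges that the child cannot continue, the 3 × ULN figure is an example, and the reference to Section 16.2 sends the reader to the table. An investigator who observes a well child at 4 × ULN breaches neither passage. This is correct as far as it goes. A reader might infer that 9.1.1 imposes a fixed stop above 3 × ULN, and the documents do not support that. What remains is that the example and the table it cites give different guidance for the same finding.

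A reader might also infer that Table 16-3 merely observes children above 3 × ULN. It does not. It stops treatment at once when there are symptoms, and its footnote counts malaise, fatigue, abdominal pain, nausea and vomiting among them. The mismatch is confined to children without symptoms, INR above 1.5 or Hy's Law features.

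It can be said that a condition that is never met misclassifies nobody, and that judgement under 9.1.1 remains available at 5–8 × ULN. Both are true. The table row still states a stopping condition that has no function in this trial.

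Finally, excluding under-dosed children is what a PPS is for, and the primary analysis is repeated on the FAS. That stands in the main. One qualification is that Section 9.1.1 allows rescue after a stop, and SAP Table 5-13 (criterion 6) counts a non-study antimalarial during the treatment period as non-response in its ITT columns, so the FAS repeat is not wholly untouched.

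**Conclusion.** The point holds for a defined band: AST/ALT above 3 and up to 8 × ULN without symptoms, INR above 1.5 or Hy's Law features, with the result known while doses remain. There the passages are not aligned, and the 2-week condition cannot be met during dosing in either arm. Both findings come from the text and the stated course length alone.

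The PPS consequence is secondary. Any lost full daily dose of KAF156/LUM-SDF takes a child out of the PPS, while a Coartem child can lose the last dose and stay in, so the same liver stop need not act alike in the two arms. It would be tempting to conclude that the primary result depends on which passage a site follows. The documents do not support that, because the number of children in the band is not given and cannot be derived. If it is one or two per group, power changes by less than one percentage point. This review takes no view on which threshold or rule is right.

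**What to change.** Reconcile Section 9.1.1, Section 10.2.1 and Table 16-3 with each other and with the 2–3 day treatment duration, including the 2-week condition in the row above 5 and up to 8 × ULN. After that, an investigator should find the same instruction for a given AST/ALT result on a dosing day whichever passage is read first. The choice of threshold and rule belongs to the sponsor's safety team.

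The cost is a protocol wording change and a notice to sites. The sample size, PPS definition and analysis methods are unaffected.
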